1. * Describe the purpose, specific aims, or objectives and state the hypotheses to be tested:

The purpose of this study is to assess the efficacy of Theraworx foam in reduction of inflammation and pain as measured by subjective pain/disability scales, motion, and strength testing.

Specific Aim 1: To assess the efficacy of Theraworx foam in reduction of pain on subjective pain/disability scales for thumb CMC arthritis.

- Hypothesis 1a: Patients given the Theraworx foam and compression wrap will see significant improvements in reported Numeric Pain Rating Scale (NPRS) compared to patients who are given the placebo foam and compression wrap and Theraworx foam alone.
- Hypothesis 1b: Patients given the Theraworx foam and compression wrap will see significant improvements in score on the Disabilities of the Arm, Shoulder, and Hand (DASH) questionnaire compared to patients who are given the placebo foam and compression wrap and Theraworx foam alone.

Specific Aim 2: To assess the efficacy of Theraworx foam to improve function and patient reported outcomes for thumb CMC arthritis.

- Hypothesis 2a: Patients given the Theraworx foam and compression wrap will see significant improvements wrist range of motion compared to patients who are given the placebo foam and compression wrap and Theraworx foam alone.
- Hypothesis 2b: Patients given the Theraworx foam and compression wrap will see significant improvements in grip and pinch strength compared to patients who are given the placebo foam and compression wrap and Theraworx foam alone.

2. * Describe the relevant prior experience and gaps in current knowledge including preliminary data. Provide for the scientific or scholarly background for, rationale for, and significance of the research based on existing literature and how it will add to existing knowledge:

Recent research surrounding the structure and function of the outermost layers of

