Significance: If the Theraworx foam and/or Theraworx foam with compression wrap can be shown to reduce pain and allow for improved functional measures, the product can be proposed as an option for conservative treatment of thumb CMC OA and reduce the reliance on oral pain medications, steroid injections, and surgery.

Study Design

1. Total number of subjects to be enrolled at this site (enter -1 for chart reviews, banking, registries):

60

2. Describe and explain the study design:

After informed consent, subjects will be randomized to one of three groups:

1. Theraworx foam with compression wrap
2. Placebo foam with compression wrap
3. Theraworx foam alone

Baseline testing will include Numeric Pain Rating Scale (NPRS). The Disabilities of the Arm, Shoulder, and Hand (DASH) will be administered to the participant by the study coordinator. Static range of motion will be tested with a wrist goniometer measuring flexion, extension, ulnar deviation, and radial deviation with the participant's elbow supported on a hand table. Strength testing will be performed with a hand dynamometer and pinch meter. These questionnaires/tests will be performed at baseline, 1 week, and 2 week visits. They should take approximately 10 minutes to complete.

Subjects will be instructed to apply the foam every night (two pumps and rub into the base of the thumb). This will be demonstrated by the research coordinator (to be hired and added to this IRB application).

Participants will be asked to apply the foam nightly for a minimum of 6 and maximum 10 of hours and avoid use of lotions, topical creams, or topical NSAIDs during the study period. Subjects will be advised to avoid other oral prescription or OTC pain relief medications during the 2-week study period. A study data sheet will be given at this time for the participant to document nightly compliance hours, daily Tylenol use, and daily pain rating. This sheet will be collected at the 2 week visit. This portion of the research visit should take approximately 5 minutes but will allow for time for questions.

Randomization will occur via block randomization designed to randomize subjects into groups that result in equal sample sizes.

3. Describe the primary and secondary study endpoints:

All endpoints are primary:

1. Numeric Pain Rating Scale
2. Disabilities of the Arm, Shoulder, and Hand (DASH)
3. Pinch strength
4. Grip strength
5. Thumb range of motion

4. Provide a description of the following study timelines:

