Duration of an individual subject's active participation:

2 weeks

Duration anticipated to enroll all subjects:

1 year

Estimated date for the investigator to complete this study (complete primary analyses):

9/30/2019

5. List the inclusion criteria:

Patients of [name], the PI, with the following:

1. Thumb CMC arthritis
2. greater than or equal to age 18
3. Interested in non-operative treatment of thumb arthritis

6. List the exclusion criteria:

1. Recent corticosteroid injection into the thumb joint
2. Non-English speaking
3. skin lesions or rashes on the thumb
4. current use of topical anti-inflammatory medications
5. concomitant thumb/wrist diagnoses that would impact the results (as determined by the PI)
6. known allergy to magnesium

7. Will children or any gender, racial or ethnic subgroups be explicitly excluded from participation?

Yes No

* Identify the subgroups and provide a justification:

Children - arthritis of the thumb CMC joint does not typically exist in subjects less than the age of 18 and including a rare patient that might have CMC arthritis would bias our results.

8. Describe the power analysis used and cite your method of statistical analysis. If a power analysis is not possible, thoroughly justify the sample size required for the study, including appropriate literature citation (alternatively provide page reference in attached protocol):

The mean pain reported in subjects with CMC arthritis is 5 (out of 10) on the numeric pain rating scale. Assuming a clinical meaningful change in pain of 2 on this scale, an alpha of 0.05 and beta of 0.2, the power analysis demonstrates 16 subjects required per group. Assuming a drop out rate of 20%, we will enroll 20 subjects per group.

Research Activities

- 1. * Provide a detailed description of all research activities (including screening and follow-up procedures) that will be performed for the purpose of this research study. This description of activities should be complete and of sufficient detail to permit an assessment of associated risks.**

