There may be a direct benefit for participating in this study, if the study hypothesis is true, there is a chance that the treated wrap will provide more pain relief and inflammation reduction than the placebo wrap/bracing alone.

The data gathered will allow us to determine if there is a benefit to the test foam in reducing pain and inflammation in thumb

CMC OA. Having an understanding of the product in recovery may lead to future studies that investigate a wider array of measures related to conservative CMC OA treatment.

7. Do you anticipate any circumstances under which subjects might be withdrawn from the research without their consent?

Yes No

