*** Describe the circumstances and any procedures for orderly termination:**
unforeseen illness or allergic reaction to foam or non-compliance

8. Describe procedures that will be followed when subjects withdraw from the research, including partial withdrawal from procedures with continued data collection and data already collected:

The data already collected will continue to be used in the study.

Placebo Arm

1. * Is there a commonly used diagnostic/treatment approach that is currently recognized as being effective for the proposed subjects' disease or condition, and that will be withheld from subjects assigned to the placebo arm of this research study:

Yes

2. Describe the commonly used diagnostic/treatment approaches that will be withheld from subjects assigned to the placebo arm of this research study:

A commonly used treatment approach is corticosteroid injection, over the counter pain medications, and/or surgical treatment.

3. Is enrollment into this study limited to individuals in whom the commonly used diagnostic/treatment approaches are known to be ineffective or intolerable?

no

4. Provide a scientific justification for the placebo-control arm of this research study:

The study purpose is to compare the use of TheraWorx foam and compression wrap, with the placebo foam with wrap and Theraworx foam alone on subjects with thumb carpometacarpal osteoarthritis having thumb or wrist pain.

5. How long will subjects participate in the placebo arm? Justify why this duration is necessary:

2 weeks. This is a short period of time. If no benefit in the placebo arm, can efficiently undergo other treatment options such as steroid injection.

6. How frequently will the subject's condition or disease be monitored and compare that to the frequency of monitoring associated with standard care for this disease/condition?

weekly

7. What specific endpoints will result in discontinuing a subject's participation due to worsening of the subject's disease or condition?

It is such a short study and examining a chronic condition (arthritis) that the PI does

not expect an acute worsening of the disease or condition.

8. What is the risk to subjects who receive no active treatment for their disease or condition while in the placebo arm?

Delay in treatment by usual care conservative measures resulting in pain

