9. Describe the planned involvement of a 'contact person' who interacts with the subject on a regular basis and who will notify the investigators immediately of any problems related to the subject's disease or condition:

There is no reason why the subject could not contact the investigators in this study on thumb arthritis. No plans to involve a contact person.

Note: The involvement of the contact person must also be addressed in the consent form

Statistical Analysis Plan

The Primary Outcome is VAS pain score at 2 weeks

This will be analyzed with ANOVA which is the appropriate test for continuous data and multiple groups.

Significance will be set at 0.05

Secondary Outcomes

Will also be analyzed using ANOVA.

Significance will be set at 0.05

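### The SAP names a three-group ANOVA and no contrast, so no planned test separates the two comparisons in Hypothesis 1a or decides the foam claim

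*Combined protocol and SAP*

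**What the plan says.** The Statistical Analysis Plan is a few lines long. It names pain at 2 weeks as the primary outcome and says "This will be analyzed with ANOVA which is the appropriate test for continuous data and multiple groups". Significance is 0.05, and secondary outcomes are handled the same way. It names no pairwise comparison, contrast, follow-up procedure, testing order or multiplicity rule, and neither does any other section.

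The trial's questions are more specific:
- Study Aims, item 1, Hypothesis 1a predicts that foam plus wrap will show "improvements in reported Numeric Pain Rating Scale (NPRS) compared to patients who are given the placebo foam and compression wrap and Theraworx foam alone". Hypotheses 1b, 2a and 2b have the same structure.
- Placebo Arm, item 4 gives the purpose as to "compare the use of TheraWorx foam and compression wrap, with the placebo foam with wrap and Theraworx foam alone".
- Study Aims, item 1 opens with "The purpose of this study is to assess the efficacy of Theraworx foam in reduction of inflammation and pain", and Risk and Benefits, item 6 says "The data gathered will allow us to determine if there is a benefit to the test foam in reducing pain and inflammation".

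Study Design, item 8 gives the sample size: "an alpha of 0.05 and beta of 0.2, the power analysis demonstrates 16 subjects required per group". The effect is 2 points on the 0 to 10 pain scale, with 20 enrolled per group to allow for 20% dropout. Neither an SD nor a test is stated.

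**The concern.** Call the arms A (foam plus wrap), B (placebo foam plus wrap) and C (foam alone). Only A versus B holds the wrap constant and varies the foam, so it is the comparison that answers the foam question. A versus C shows what the wrap adds.

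The F test's null, A = B = C, is the joint null of those two comparisons, so the test is not irrelevant to them. But it rejects for any pattern of differences in any direction. A significant result would not say whether the foam, the wrap or both made the difference, nor whether foam plus wrap was the better arm. The step from the F test to a conclusion about the foam is left open, so the pair, the order and any adjustment could be chosen after the data are seen.

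**Working it through.** **Inputs.** From Study Design, items 2 and 8: three equal arms, 2-point effect, reference mean 5, alpha 0.05, power 80%, 16 completers per arm. Assumed, because the documents give none: a common SD of 2, with range 1.5 to 3. Assumed, because sidedness is not stated: two-sided tests. Lower scores are better, so a benefit of 2 points is shown as a mean of 3 against 5.

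**1. The plan's 16.** For two means, n = 2·SD²·(1.960 + 0.842)²/2². At SD 2 this is 2 × 4 × 7.849/4 = 15.7, rounded up to 16. Any SD from about 1.96 to 2.02 gives 16, and 16/0.8 = 20 enrolled. The three-group F test with one arm differing by 2 also needs 16 at SD 2. The stated figure therefore does not show which test was powered.

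**2. F test power.** The noncentrality is λ = n·Σ(mean − grand mean)²/SD². For means 3, 5, 5 the grand mean is 4.333 and the sum of squares is 1.778 + 0.444 + 0.444 = 2.667, so λ = 16 × 2.667/4 = 10.67. The means 3, 3, 5 and 3, 5, 3 also give 2.667. With 2 and 45 df (critical value 3.204), power is 81.4% in all three cases.

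**3. What the contrasts show in the same cases** (SD 2, pooled three-group error, 400,000 simulated trials per case; contrasts counted when significant in favour of A):

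| Truth (A, B, C) | F significant | A beats B | A beats C | Both |
|---|---|---|---|---|
| Hypothesis 1a true (3, 5, 5) | 81% | 79% | 79% | 68% |
| Only the wrap works (3, 3, 5) | 81% | 2.5% | 79% | 2.5% |
| Only the foam works (3, 5, 3) | 81% | 79% | 2.5% | 2.5% |

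In the wrap-only case, F is significant without a win for A over B in 79% of trials.

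**4. Sensitivity.** F test rejection when only the wrap works:

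| Wrap effect | SD 1.5 | SD 2 | SD 2.5 | SD 3 |
|---|---|---|---|---|
| 2 points | 97% | 81% | 61% | 45.5% |
| 1.5 points | 81% | 55% | 38% | 27% |
| 1 point | 45.5% | 27% | 19% | 14% |

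**5. Power for the comparisons that matter.** For A versus B the noncentrality is 2/(SD·√(2/16)), which is 2.828 at SD 2. Against a critical t of 2.014 on 45 df, power is 79.0%. With 2-point effects on both comparisons:

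| | SD 1.5 | SD 2 | SD 2.5 | SD 3 |
|---|---|---|---|---|
| Foam contrast | 96% | 79% | 60% | 45% |
| Both contrasts | 93% | 68% | 44% | 29% |

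**6. Error when all arms are equal,** if either contrast may support a claim: 9.0% with both tested unadjusted, 5.0% in fixed order, and 4.2% when contrasts are read only after a significant F test.

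**The case against.** The strongest reply is that contrasts are routinely taken from a fitted ANOVA, and that the SAP neither makes the F test its decision rule nor rules out follow-up comparisons. That stands. A reader might infer that the sponsor will treat a significant F as proof that the foam works, so that 81% is a false-claim rate. The documents do not say so. In the wrap-only case the F test correctly rejects a false null, and a false foam claim would also require ignoring A versus B. What remains is that no contrast is named, and step 6 shows that the choice changes the error rate.

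A reader might also take "If the Theraworx foam and/or Theraworx foam with compression wrap can be shown to reduce pain", in the Significance paragraph, to mean that a win on either comparison is enough. That phrase joins two products, not two comparisons. Hypothesis 1a joins its comparators with a plain conjunction, which implies that both must succeed. Two tests that must both succeed need no alpha split, so a missing multiplicity rule matters only if one win may support a claim.

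Nor should the F test be ruled out as a first step. With three arms, contrasts read only after a significant F hold the error within 5%. They keep about 74% power for a foam-only or a wrap-only effect at SD 2, against 79% without the gate. For the full hypothesis the gate costs under one point. Using it or not is a trade-off.

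Finally, the Brief description calls this a pilot. But the aims are stated as efficacy hypotheses, the sample size targets 80% power, and the Significance paragraph would propose the product as a treatment option on a positive result.

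**Conclusion.** The point holds as a gap in the analysis plan. The design is not at fault: its arms allow the foam effect and the wrap effect to be estimated separately. The only named analysis does not separate the two comparisons in Hypothesis 1a, and no rule says which result supports a foam claim. At 16 completers per arm, an assumed SD of 2 and a 2-point difference in one arm, the F test gives the same 81% for three different truths. The 2-point wrap effect in the illustration is borrowed from the sample-size text, and the figure falls with a smaller wrap effect or a larger SD. At SD 2 the stated 80% power is not met for the full hypothesis (68%) and is narrowly missed for the foam contrast (79%). At SD 1.5 both exceed 80%.

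**What to change.** In the Statistical Analysis Plan:
- Pre-specify two contrasts from the same three-group model, each two-sided at 0.05: foam plus wrap versus placebo foam plus wrap, and foam plus wrap versus foam alone.
- State that a foam claim rests on the first, and that the full Hypothesis 1a needs both in favour of foam plus wrap, with no alpha split.
- If either contrast alone may support a claim, name the rule. Fixed order with the foam contrast first, or contrasts only after a significant F test, are both acceptable.
- Report both differences with 95% CIs, and use the same contrasts for the other endpoints.

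In Study Design, item 8, state the SD and the test behind the 16, and restate power for these contrasts.

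Two matters need separate treatment. One is multiplicity across the five endpoints, since Study Design, item 3 says "All endpoints are primary". The other is the pain scale, which is VAS in the SAP and NPRS elsewhere.

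**Cost.** The change is to wording, and no patients are added if the lower power is accepted. Holding 80% for both contrasts at SD 2 would take about 21 completers per arm (20 give 79.5%). That is 21/0.8 = 26.25, so 27 enrolled per arm and 81 in total instead of 60. Under the fixed order, if only the wrap works, a formal wrap claim is reached in about 2.5% of trials at SD 2, against 79% if that contrast were tested alone. Its estimate and CI would still be reported.

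### The ANOVA of 2-week pain leaves out the baseline score the trial already collects, which costs precision; the secondary time point and the handling of missing week-2 scores are also unstated

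*Combined protocol and SAP*

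**What the plan says.** The SAP is a few lines at the end of the document. It sets the primary outcome ("The Primary Outcome is VAS pain score at 2 weeks") and the method ("This will be analyzed with ANOVA which is the appropriate test for continuous data and multiple groups"), at a significance level of 0.05. For secondary outcomes it adds "Will also be analyzed using ANOVA", again at 0.05. It names no covariate, change score, repeated-measures term, analysis set or rule for a missing score, and gives no time point for the secondary outcomes.

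Study Design item 2 gives the schedule: "These questionnaires/tests will be performed at baseline, 1 week, and 2 week visits". Research Activities item 1 repeats it. Both call the pain measure the NPRS, where the SAP says VAS.

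Study Design item 8 plans 16 evaluable participants per group, inflated to 20 for 20% dropout. On withdrawal, Risk and Benefits item 7 asks about circumstances in which "subjects might be withdrawn from the research without their consent", and the answer is "unforeseen illness or allergic reaction to foam or non-compliance". Item 8 asks about withdrawal procedures, "including partial withdrawal from procedures with continued data collection and data already collected". The answer is one sentence: "The data already collected will continue to be used in the study".

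**The concern.** Basic Information item 3 calls this a pilot. With about 16 completers per arm, what it can deliver is an estimate with an interval, and the width of that interval matters. The baseline scores that would narrow it are already being collected, but the stated analysis does not use them.

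For the secondary outcomes, a single-visit score, a change score and a repeated-measures analysis are all compatible with the text, so the choice stays open after the data are seen.

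The second issue is who contributes. An ANOVA of observed week-2 scores leaves out anyone without one and makes no use of that person's week-1 score. This sits awkwardly with the statement that collected data stay in use. The daily pain sheet does not help as written, because it is handed in at the 2-week visit. If leaving is related to pain, the comparison of those who remain can be shifted.

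**Working it through.** **Inputs from the documents.** Difference 2 points, alpha 0.05, power 80%, 16 evaluable and 20 enrolled per group, 20% dropout (Study Design item 8); three equal groups, 60 in total (Study Design items 1 and 2).

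**Assumed.** The SD and the correlation r between baseline and week-2 pain are not stated, so both are ranged.

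**Plan's own figure.** The two-group formula n = 2 × (1.960 + 0.842)² × (SD/2)² gives 15.7, rounded up to 16, at SD 2. The plan's 16 therefore fits SD 2, but cannot be confirmed because no SD is given. Dropout: 16/(1 − 0.2) = 20 per group, and 3 × 20 = 60. Expected without a week-2 score: 60 × 0.20 = 12.

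**Precision without baseline (SD 2, 16 per arm).** Standard error of a contrast = 2 × √(2/16) = 0.707. Noncentrality = 2/0.707 = 2.83 on 45 df, which gives power 79%. Half-width = 2.014 × 0.707 = 1.42.

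**Precision with baseline.** The residual SD is 2 × √(1 − r²), one error df is lost (44 remain), and estimating the slope inflates the standard error slightly, by about √(1 + 1/43). Simulated three-arm ANCOVA, per pairwise contrast at an unadjusted 0.05:

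| | No baseline | r = 0.3 | r = 0.5 | r = 0.7 |
|---|---|---|---|---|
| Power, SD 1.5 | 96% | 97% | 99% | >99% |
| Power, SD 2 | 79% | 82% | 88% | 97% |
| Power, SD 2.5 | 60% | 63% | 72% | 87% |
| Half-width, SD 2 | 1.42 | 1.37 | 1.24 | 1.02 |

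At SD 2 the break-even is near r = 0.15. At r = 0 power is 78%, a loss of about 1 point.

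**Overall three-arm F-test (SD 2, one arm differing by 2).** λ = 16 × [(4/3)² + 2 × (2/3)²]/4 = 10.7, which gives power 81%. Dividing λ by 1 − r² and losing one df gives 85%, 91% and 98%. With evenly spaced means (0, 1, 2) the sequence is 69%, then 73%, 81% and 94%.

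**Multiplicity.** With three arms of 16, testing each contrast at 0.05 with no overall test gives a familywise error of about 9% for two contrasts and 12% for three.

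**Dropout, illustrative (SD 2).** First, 20% is lost in each arm, and only in the foam-plus-wrap arm do the odds of leaving rise with pain, by 0.5 to 1 log-odds per SD. The assumed correlations (baseline with each week; week 1 with week 2) are (0.3; 0.5), (0.5; 0.7) and (0.7; 0.8). Overstatement of benefit, in points:

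| Leaving depends on | ANOVA | ANCOVA | Mixed model |
|---|---|---|---|
| week-1 pain, all leave after week 1 | 0.10–0.28 | 0.06–0.16 | about 0 |
| week-1 pain, half leave before that visit | 0.09–0.28 | 0.06–0.16 | 0.03–0.07 |
| week-2 pain | 0.19–0.35 | 0.10–0.32 | 0.06–0.26 |

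The largest shift relative to the half-width is 0.35/1.42 = 0.25.

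Second, one identical rule on week-2 pain in both arms, with a true 2-point effect and 20% lost overall. The arm with more pain loses more (24% v 16% at log-odds 0.5, 27% v 13% at 1), and the ANOVA contrast moves 0.07 to 0.22 points towards no effect. Third, no true effect, the same slope, but 10% v 30% lost: the shift is 0.19 to 0.32. With the same slope and the same loss rate in both arms it is about 0.

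**The case against.** The strongest reply is that nothing here is wrong as analysis. A three-group ANOVA is valid under randomisation, its overall F-test is a single test at 0.05, and the primary outcome and time point are stated. That stands. A reader might infer that omitting baseline biases the comparison; the documents do not support this, because allocation is randomised and only precision is lost.

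Enrolling 20 to keep 16 covers the planned loss. That also stands, so the 12 missing scores are not a power shortfall against plan. Enrolment does not address which participants leave.

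The retention sentence on withdrawal might be taken as a missing-data rule. It keeps data, but does not say what the week-2 analysis does when that score is absent. Equally, the SAP does not say that such participants are dropped. That is the usual default for an ANOVA, and imputation is not excluded.

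The word also in the secondary-outcome sentence may carry over the 2-week time point. That is a fair reading, but it is not stated, and there are two post-baseline visits.

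A mixed model adds little power over ANCOVA. With 4 of 20 per arm leaving at random after week 1 it gives 83%, 91% and 98%, against 82%, 88% and 97%, and there is no gain if all leave before week 1. It is therefore optional.

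**Conclusion.** The point holds as a recommended improvement. Its core is the missing baseline covariate: a gain of about 3, 9 and 18 power points per contrast at r = 0.3, 0.5 and 0.7, and at r = 0.5 an interval about 12% narrower (1.24 against 1.42). This rests on the assumed SD of 2 and on r. The gain disappears near r = 0.15.

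The unstated secondary time point and missing-score rule are lesser omissions. Bias from dropout is possible, not shown. It needs leaving to depend on pain, together with a difference between arms in either that dependence or the loss rate. It would be too strong to say that only a difference in dependence matters, since one common rule with a real treatment effect already produces unequal losses. It would also be too strong to call the trial's result unreliable on this ground: the largest illustrated shift is about a quarter of the half-width.

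**What to change.** 1. Reconcile the name of the pain scale (VAS in the SAP, NPRS in Study Design item 2 and Research Activities item 1), so that covariate and outcome are the same measure.
2. Replace the ANOVA with an ANCOVA of the week-2 score on arm and baseline, in all randomised participants with data, analysed in their assigned arms. Keep the overall three-arm test at 0.05 as primary. Interpret pairwise contrasts only if it is significant, or adjust them for multiplicity. Name week 2 and the same model for DASH, grip, pinch and motion.
3. Optionally, use a mixed model of weeks 1 and 2 (arm, visit, arm-by-visit, baseline, baseline-by-visit) so that leavers' week-1 scores contribute. It reduces but does not remove bias when leaving depends on unobserved pain, and recovers no one without a post-baseline visit.
4. Report losses and reasons by arm, and add one sensitivity analysis with shifted imputations, for example 0 to 2 points. A 2-point shift in 20% of one arm moves the contrast by 0.20 × 2 = 0.4.
5. Ask the sponsor to clarify, under Risk and Benefits items 7 and 8, whether participants withdrawn for non-compliance are still assessed at week 2. The present answer covers only data already collected.

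The cost is SAP wording, a clarification in the withdrawal section, one degree of freedom (a few more parameters for the mixed model) and a little more analysis work. About 1 point of power is lost if baseline turns out to be uncorrelated with week 2.
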